	
changes in hCG+β in predicting clinical pregnancy on day 21 (+4/-3) and ongoing pregnancy on day 65 (+7).
 
 7. To determine, based on the AUCs of the ROC curves, whether changes in hhCG on day 7 (+1) vs. day 4 (+1) are superior to corresponding changes in hCG+β in predicting pregnancy on day 11 (+2) defined by serum hCG+β. 8. To compare the sensitivity and specificity and the positive and negative predictive value of changes in hhCG with those of hCG+β on day 7 (+1) vs. day 4 (+1) and day 11 (+2) vs. day 7 (+1) for clinical pregnancy on day 21 (+4/-3) and ongoing pregnancy on day 65 (+7). 9. To compare the sensitivity and specificity and the positive and negative predictive value of changes in hhCG with those of hCG+β on day 7 (+1) vs. day 4 (+1) for pregnancy on day 11 (+2) defined by serum hCG+β. 10. To determine the course of hhCG and hCG+β from day 4(+1) through day 11(+2) 11. To determine the usefulness of absolute values and changes in hhCG over time in distinguishing between the 5 disjunct pregnancy categories of 1) negative pregnancy, 2) ectopic pregnancy, 3) 1st trimester miscarriage 4) ongoing pregnancy on day 65 (+7) and 5) biochemical pregnancy. 12. To investigate into differences in the course of hhCG values between single and multiple pregnancies (if warranted by the number of multiple pregnancies) 13. To determine incidents and indirect harms. 
*All days mentioned above are counted from ET (=Day 0).

TARGET STUDY POPULATION	
Inclusion criteria:
 
 • Written informed consent • Patients undergoing their first or second IVF-ET cycle • Age 18-45 years • Use of Ovitrelle for final follicular maturation and luteinization in the case of fresh ET • Fresh or frozen day-5 blastocysts transfer (autologous or egg donation)

	
Exclusion criteria:
 
 • Gestational surrogacy (patient's eggs used for pregnancy in a surrogate mother) • Canceled IVF cycles • GnRH agonist triggering cycles in the case of fresh ET
STUDY DURATION PLANNED	
Clinical part of the study: from June 2017 to April 2018
 
Patient recruitment time: from June 1, 2017 to Dec 31, 2017

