- Taking of a further 6 mL of venous blood for asservation of 0.5 mL of serum (to be kept in the freezer at -80°C with temperature log and shipped in batches for the central analysis of hhCG), of a further 0.5 mL for IVI kept in the freezer at -80°C and of another of 2.0 mL kept in the freezer at -80°C for to be shipped to Roche at the end of the study.
- Concomitant diseases and medication.

Visit 3

At Visit 3 the following will be done and documented in the eCRF:

- Measurement and documentation of serum estradiol, progesterone and hCG+ß by the study site
- Separation of 6 mL of blood taken in addition to routine blood sampling for asservation of 0.5 mL of serum (to be kept in the freezer at -80°C with temperature log and shipped in batches for the central analysis of hhCG), of a further 0.5 mL for IVI kept in the freezer at -80°C and of another 2.0 mL kept in the freezer at -80°C for to be shipped to Roche at the end of the study.
- Concomitant diseases and medication.

Visit 4

At Visit 4 the following will be done and documented in the eCRF:

- Concomitant diseases and medication
- Ultrasound for detection of embryo sac, (heart beat) or ectopic pregnancy.

Visit 5

At Visit 4 the following will be done and documented in the eCRF:

- Concomitant diseases and medication
- Ultrasound for detection of embryo sac, heart beat or ectopic pregnancy.

Visit 6

At Visit 5 the following will be done and documented in the eCRF:

- Concomitant diseases and medication
- Documentation of pregnancy category: negative pregnancy, ectopic pregnancy, 1st trimester miscarriage, ongoing pregnancy (single/multiple) on day 65 (+7), biochemical pregnancy (see section 5.1)
- Incidents and indirect harms
- Final documentation.

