5.1 Pregnancy Endpoints

The study will have to use various pregnancy endpoints for various analyses. For the analysis of the primary objective and some of the secondary objectives the endpoint will be clinical pregnancy on day 21* (+4/-3) defined as detection of embryo sac by US, regardless of whether or not there will be a miscarriage during the later course of the 1st trimester. For some other secondary objectives the endpoint will be ongoing pregnancy on day 65 (+7) defined as detection of fetal heart beat by US at this time point or later). Detection of embryo sac/fetal heart beat on day 65 (+7) replaces missing detection of embryo sac on day 21 (+4/-3) for the definition of clinical pregnancy.

For pregnancy on day 11 (+2) as an individual endpoint and for the allocation of patients to categories as described below (negative and biochemical pregnancy in particular) a cut-off value for hCG+β on day 11 (+2) of >10 mIU/mL will be used as per practice at the study site.

For the purposes of the analysis with respect to secondary objective no. 11 there will be 5 disjunct pregnancy categories:

1) Negative pregnancy

hCG+β on day 11 (+2) ≤10 mIU/mL, unless clinical pregnancy, ectopic pregnancy, ongoing pregnancy or 1st trimester miscarriage are detected at a later stage

2) Ectopic pregnancy

Rules out the remaining categories 3), 4) and 5)

3) 1st trimester miscarriage

Rules out (supersedes) categories 4) and 5)

4) Ongoing pregnancy on day 65 (+7)

5) Biochemical pregnancy

hCG+ β >10 mIU/mL on day 11 (+2) and no clinical/ongoing pregnancy at any stage and no ectopic pregnancy and no signs or symptoms of a 1st trimester miscarriage.

The following patients are ineligible for the analysis with respect to secondary objective no. 11: hCG+ β on day 11 (+2) >10 mIU/mL, missing data on ectopic pregnancy/ presence of embryo sac, fetal heart beat and no 1st trimester miscarriage.

1st trimester miscarriage will always be assumed in cases with detection of embryo sac on day 21 (+4/-3) and no ongoing pregnancy on day 65 (+7). It should be noted that per-protocol patients with this constellation will be included in the group of subjects with clinical pregnancy on day 21 (+4/-3) for the primary analysis of the study.

*All days mentioned in this section are counted from ET (=Day 0).

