7.3 Groups for Biostatistical Analysis

The population of **patients enrolled** will include all patients who gave informed consent.

The **patients treated** population will consist of all patients for whom the IVF-ET was performed.

The per-protocol population will consist of all eligible patients treated, i.e. will be restricted to those patients of the **patients treated** population who did not violate any eligibility criteria and who have available measurements for both hhCG and hCG+ β on day 4* (+1) and an assessment of clinical pregnancy on day 21* (+4/-3). A missing assessment of clinical pregnancy on day 21 (+4/-3) can be replaced by an assessment of ongoing pregnancy on day 28 (+4/-3) and/or 65 (+7).

In case of sufficiently high numbers of multiple pregnancies, subgroup analyses may be performed for patients with multiple and single pregnancies. Further subgroups of interest, if any, will be defined in the Statistical Analysis Plan.

*All days mentioned in this section are counted from ET (=Day 0).

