7.4 General Biostatistical Approaches

For the pregnancy tests based on hCG and hCG+ β levels, ROC analyses will be performed. The predicted results of the test (positive or negative, i.e. pregnant or not pregnant) will be compared to the actual presence/absence of pregnancy as observed (e.g. clinical pregnancy on day 21* (+4/-3) or ongoing pregnancy on day 65 (+7)). There are the following possibilities for the test results and observed results:

		Observed	
		Positive	Negative
Test	Positive	True positive (TP)	False positive (FP)
	Negative	False negative (FN)	True negative (TN)

For the test concerned, the rate of true positives and true negatives can be regarded in two different ways: in relation to the observed positives and negatives and in relation to the predicted positives and negatives.

Based on the observed positives and negatives, the rate of true positives is called the **sensitivity** and the rate of true negatives is called **specificity**, i.e.:

$$\text{Sensitivity} = \text{TP} / (\text{TP} + \text{FN})$$

$$\text{Specificity} = \text{TN} / (\text{TN} + \text{FP})$$

Based on the predicted positives and negatives, the rate of true positives is called the **positive predictive value (PPV)**, and the rate of true negatives is called the **negative predictive value (NPV)**, i.e.:

$$\text{PPV} = \text{TP} / (\text{TP} + \text{FP})$$

$$\text{NPV} = \text{TN} / (\text{FN} + \text{TN})$$

Sensitivity, specificity, positive and negative predictive values are all dependent on the definition of the test concerned. Receiver operating characteristics (ROC) curves are used to visualize sensitivity and specificity for various thresholds for the pertinent test: Sensitivity is plotted against 1-specificity and thus displays the test's characteristics for various cut-offs. Tests can be compared by looking at summary measures for the ROC curves, e.g. the area under the curve (AUC). Since high sensitivity and specificity are wanted in a test, a bigger area under the curve is desirable.

To define a test for practical use, a threshold has to be chosen, i.e. a cut-off that defines that values below are considered as negative test results and values above as positive test results. A threshold should be chosen as a point that optimizes the combination of sensitivity and specificity which can be done via the ROC curve by choosing the point with the least distance to the upper left corner which stands for specificity = 100% and sensitivity = 100%.

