7.6.2 Secondary Study Objectives

In addition to the comparison of the AUCs under the ROC curves for day 4*, the same analyses will be performed for the hhCG and hCG + β tests at days 7 and 11 with respect to predicting clinical pregnancy on day 21*; at days 4, 7 and 11 with respect to predicting pregnancy on day 65; at days 4 and 7 with respect to predicting pregnancy on day 11. The same methods as for the analysis of the primary objective will be applied here.

For the comparisons of sensitivity and specificity and the positive and negative predictive values at various time points with respect to pregnancy at various later time points, the following approach will be used:

Optimal thresholds for the two tests and the various time points will be identified from the pertinent ROC curves for the time point (day 4, 7 or 11) and endpoint (pregnancy at day 65,

21 or 11) considered. The optimal threshold for the time point and test at hand will be found using Youden's index (sensitivity + specificity -1), choosing the point for which the index is maximal.

The thresholds and the corresponding sensitivities and specificities will be summarized for each time point, pregnancy endpoint and test. Pertinent positive and negative predictive values will be shown for the same thresholds for the various time points.

The course of hhCG and hCG + β over time will be summarized by descriptive summary statistics (mean, standard error of the mean, median, Q1, Q3, minimum and maximum) for the disjoint pregnancy outcome categories as defined in 5.1. If there are sufficiently many multiple pregnancies, the same analysis will be performed for the categories of multiple and single pregnancies (irrespective of pregnancy outcome).

Incidents and indirect harms will be summarized by absolute and relative frequencies.

*All days mentioned in this section are counted from ET (=Day 0).

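### Section 5.1, read literally, codes a sac-positive woman with no day-65 outcome information as a 1st trimester miscarriage, which can contaminate the descriptive objective 11 summaries

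*Combined protocol and SAP*

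**What the plan says.** Four pieces of text in the combined protocol and SAP bear on this point.

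- **The rule (5.1).** A first-trimester "miscarriage will always be assumed in cases with detection of embryo sac on day 21 (+4/-3) and no ongoing pregnancy on day 65". The same section says that such women stay in the clinical-pregnancy group for the primary analysis.
- **The definition it depends on (5.1).** The endpoint is "ongoing pregnancy on day 65 (+7) defined as detection of fetal heart beat by US at this time point or later". This is a positive finding; no separate status is given for a woman who was not assessed.
- **The exclusion (5.1).** For objective 11, women with day-11 hCG+β above 10 mIU/mL are ineligible if they have "missing data on ectopic pregnancy/ presence of embryo sac, fetal heart beat and no 1st trimester miscarriage". The miscarriage rule is the next sentence.
- **The use (Synopsis, secondary objective 11; 7.6.2).** The objective is "To determine the usefulness of absolute values and changes in hhCG over time in distinguishing between the 5 disjunct pregnancy categories". Section 7.6.2 summarises the course of both markers by descriptive statistics "for the disjoint pregnancy outcome categories as defined in 5.1".

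**The concern.** Absence of a detected heart beat can mean that someone looked and found none, or that nobody has any information. The rule in 5.1 does not separate the two, and its wording allows no exception. A viable pregnancy lost to follow-up would then be counted as a loss.

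Objective 11 asks how well hhCG separates the outcome categories, and the contrast between miscarriage and ongoing pregnancy is part of that. Viable pregnancies placed in the miscarriage group would pull its marker summaries towards those of the ongoing group and make hhCG look less able to tell them apart. If the miscarriage group turns out small, a few such women would be enough to matter.

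**Working it through.** **Step 1: follow one woman through 5.1.** Day-11 hCG+β is above 10 mIU/mL, a sac is seen on day 21, a heart beat is recorded on day 28, and nothing is known afterwards.

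| Category | What 5.1 needs | Met? |
|---|---|---|
| Negative | day-11 hCG+β of 10 mIU/mL or less, nothing found later | No |
| Ectopic | an ectopic finding | None documented |
| 1st trimester miscarriage | day-21 sac, no ongoing pregnancy on day 65 | Yes, read literally |
| Ongoing | heart beat detected on day 65 or later | No |
| Biochemical | no clinical pregnancy at any stage | No, a sac was seen |

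The day-28 heart beat plays no part, because 5.1 makes no use of day 28.

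**Step 2: does the exclusion remove her?**

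- If all the listed items must be missing, no: her sac result is present.
- If any one missing item is enough, and an assumed miscarriage counts as a miscarriage, no: the condition of no miscarriage fails.
- If any one missing item is enough, and only a documented miscarriage counts, she can be excluded. Even this is uncertain, because the clause names no day for the heart beat and hers was recorded on day 28.

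**Step 3: the benign reading.** If the rule means known not to be ongoing, she fits none of the five categories, and her handling rests entirely on Step 2.

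**Step 4: can such a woman occur?** Visit 5 is day 28 (+4/-3), days 25 to 32. Visit 6 is day 65 (+7), days 65 to 72. The gap is 65 − 32 = 33 to 72 − 25 = 47 days, with no visit between. The per-protocol set in 7.3 requires no day-65 assessment, and a footnote to the Schedule of Assessments foresees premature termination. She is foreseeable; how often is not stated.

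**Step 5: size, as illustration only.** The plan gives no figure on this point. The one input it supplies is the expected number of clinical pregnancies in 7.1: 0.45 × 136 = 61.2, stated as 61. All values below for losses and unknown outcomes are assumptions.

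(a) Suppose all L true losses are documented and k viable pregnancies have an unknown outcome. The false share of the coded category is k/(L + k):

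| L | k = 1 | k = 2 | k = 3 | k = 6 |
|---|---|---|---|---|
| 6 | 1/7 = 14% | 2/8 = 25% | 3/9 = 33% | 6/12 = 50% |
| 9 | 1/10 = 10% | 2/11 = 18% | 3/12 = 25% | 6/15 = 40% |
| 12 | 1/13 = 8% | 2/14 = 14% | 3/15 = 20% | 6/18 = 33% |

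At L = 9 there are 61 − 9 = 52 ongoing pregnancies, so k = 1 is 1/52 = 1.9% of them. If missingness is unrelated to the markers, the expected difference in means between miscarriage and ongoing is multiplied by L/(L + k), for example 9/12 = 0.75 at k = 3.

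(b) Case (a) treats every unknown as viable. Let D = 9 losses be documented and u = 3 women be unknown, v of them viable. The literal rule makes v/(D + u) of the category false. Leaving the unknowns out instead loses (u − v)/(D + u − v) of the true losses.

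| v | False share, literal rule | True losses left out if unknowns are dropped |
|---|---|---|
| 0 | 0/12 = 0% | 3/12 = 25% |
| 1 | 1/12 = 8% | 2/11 = 18% |
| 2 | 2/12 = 17% | 1/10 = 10% |
| 3 | 3/12 = 25% | 0/9 = 0% |

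(c) If a share l of sac-positive women is unknown and the loss rate m is the same in known and unknown women, the false share is l(1 − m)/[l + (1 − l)m]. At l = 5% and m = 15% it is 0.0425/0.1925 = 22%. Over l of 2% to 10% and m of 10% to 25% it runs from 0.015/0.265 = 6% to 0.09/0.19 = 47%.

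**The case against.** The case for leaving 5.1 alone is reasonable. The section speaks of missing data or missing detection when it means absent information, so its phrase about no ongoing pregnancy can be taken as a known status. The site records a pregnancy category for each woman at Visit 6 (2.4), and a scan after day 65 also counts, so an absent day-65 scan need not mean an unknown outcome. The exclusion may have been written for exactly these women. The output is descriptive, with no test attached. And women who vanish may be those who lost the pregnancy, in which case the rule classifies them correctly.

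Much of this stands. A benign intent is plausible, the problem is confined to women with no outcome information from any source, and the direction of any net error is unknown. It does not settle the text: the Visit 6 entry refers back to 5.1 for its categories, and the exclusion depends on there being no miscarriage while the next sentence assumes one. Two analysts could code the same woman differently.

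A reader might also infer that the day-65 accuracy analyses (objectives 2, 4, 6 and 8) are distorted. No text applies this coding there, and 7.4 says that test results "will be compared to the actual presence/absence of pregnancy as observed". Section 7.6.2 does not say how an unknown day-65 outcome is handled in those analyses, but that is silence, not this rule. Nor does the wording in 7.3, where a missing day-21 assessment may be "replaced by an assessment of ongoing pregnancy on day 28 (+4/-3) and/or 65 (+7"), support the point: it concerns entry to the per-protocol set, not miscarriage coding.

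**Conclusion.** The point holds on the literal text: 5.1 states an operative rule that can place a woman of unknown outcome in the miscarriage category, and the objective 11 exclusion does not clearly take her out. The consequence is limited to the descriptive category summaries in 7.6.2. The primary comparison is on clinical pregnancy at day 21, where 5.1 keeps these women as positives, so sample size, power and alpha are unchanged.

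The size cannot be stated. It is zero if every sac-positive woman has a known outcome, and the percentages above depend wholly on assumed loss and missing rates and on how many of the unknowns are viable. It would be wrong to conclude that the category will be contaminated by any particular amount, or that dropping the unknowns is certain to reduce bias. Severity is low. Slips elsewhere in the document over visit numbering, the final-visit ultrasound and the recruitment dates are editorial and lend no support.

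**What to change.** Three changes of wording:

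1. In 5.1, assume 1st trimester miscarriage only where a loss is documented, or where an assessment or outcome report for day 65 or later shows that the pregnancy is not ongoing.
2. In 5.1, make sac-positive women with an unknown day-65 outcome ineligible for objective 11, stated without reference to the assumed miscarriage, and report how many there are.
3. In 7.6.2, repeat the category summaries with these women coded as miscarriage, as a sensitivity display.

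The cost is about two sentences in 5.1 and one in 7.6.2, with no extra visit or procedure. The category may hold slightly fewer women, and some true but undocumented losses may be left out; the sensitivity display would show whether either matters.

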5.2 Patient Group for the Primary Analysis

The primary analysis of the study will be carried out in the per-protocol group. This will include patients who have met all inclusion criteria, violated no exclusion criterion and for whom the data for the evaluation of the primary objective have been determined in compliance with the stipulations of this protocol (i.e. valid results for hhCG and hCG+ β on day 4 (+1)* and for US on day 21* (+4/-3).Ongoing pregnancy on day 65 (+7) replaces missing US data for day 21 (+4/-3) as to the question of ongoing pregnancy on this day.

*Days mentioned in this section are counted from ET (=Day 0).

6 Patient Insurance

IVI Valencia undertakes to insure liability for potential damage caused to a subject in connection with the trial and provides insurance policy for all study subjects.

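### Protocol 5.2 and 7.3 define the primary per-protocol set differently for a woman without a day-21 ultrasound, and both put ongoing pregnancy in the place of the primary endpoint

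*Combined protocol and SAP*

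**What the plan says.** The primary analysis uses the per-protocol group, which the protocol defines in two places.

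- **5.2** requires "valid results for hhCG and hCG+ β on day 4 (+1)* and for US on day 21* (+4/-3"). For a missing scan it adds: "Ongoing pregnancy on day 65 (+7) replaces missing US data for day 21 (+4/-3) as to the question of ongoing pregnancy on this day".
- **7.3** requires an assessment of clinical pregnancy on day 21. A missing one "can be replaced by an assessment of ongoing pregnancy on day 28 (+4/-3) and/or 65 (+7").

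The endpoint itself is defined in 5.1.

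- Clinical pregnancy is a sac seen by ultrasound, "regardless of whether or not there will be a miscarriage during the later course of the 1st trimester".
- Ongoing pregnancy is a different state: "ongoing pregnancy on day 65 (+7) defined as detection of fetal heart beat by US at this time point or later".
- 5.1 has its own replacement sentence: "Detection of embryo sac/fetal heart beat on day 65 (+7) replaces missing detection of embryo sac on day 21 (+4/-3"). It concerns the endpoint only and excludes nobody.
- On miscarriage, with day 65 as the later time point: "1st trimester miscarriage will always be assumed in cases with detection of embryo sac on day 21 (+4/-3) and no ongoing pregnancy".

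Visit 5 (day 28) includes an ultrasound for sac, heart beat or ectopic pregnancy. Visit 6 (day 65) includes "Documentation of pregnancy category: negative pregnancy, ectopic pregnancy, 1st trimester miscarriage, ongoing pregnancy (single/multiple) on day 65 (+7), biochemical pregnancy", but neither the schedule nor the Visit 6 list in 2.4 includes an ultrasound there. Section 2.1 places the two ultrasounds at Visit 4 and the final visit.

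**The concern.** Two analysts, one working from 5.2 and one from 7.3, could build different primary data sets and code the same woman differently. Three features cause this.

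1. 5.2 names a state (ongoing pregnancy), while 7.3 names an assessment with either result. Under the literal reading of 5.2, inclusion depends on the outcome.
2. Only 7.3 lets the day-28 visit count. It asks there for ongoing pregnancy, which 5.1 defines only for day 65 or later and by heart beat. A sac without heart beat on day 28 would meet the primary endpoint and could still be recorded as not ongoing.
3. A woman who had a sac, missed the day-21 scan and then miscarried has no rule that restores her to the pregnant group. The automatic miscarriage rule in 5.1 needs a sac detected on day 21. The Visit 6 category could settle her case, but the protocol nowhere says that this category sets the primary outcome.

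If the choice between the rules were left until hhCG values are in hand, it would depend on the data.

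**Working it through.** **The passages side by side.** Take a woman with no day-21 ultrasound:

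| Later finding | 5.2, literal | 5.2, as day-65 status | 7.3 |
|---|---|---|---|
| Heart beat on day 65 | in, positive | in, positive | in, positive |
| Never pregnant, assessed on day 65 | out | in, negative | in, negative |
| Had a sac, miscarried before the later assessment | out | in, code not stated | in, code not stated; negative possible |
| Assessed on day 28 only | out | out | in |

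All three columns agree only in the first row.

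**The plan's own power figure (7.1).** Inputs: AUC 0.67 and 0.79, N+ = 61, N− = 75, correlation 0.6, one-sided 2.5%; stated power 0.8022.

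- Hanley-McNeil variance: V(A) = [A(1−A) + (N+ −1)(Q1−A²) + (N− −1)(Q2−A²)] / (N+ × N−), with Q1 = A/(2−A) and Q2 = 2A²/(1+A). This gives V(0.67) = 0.00220 and V(0.79) = 0.00160.
- A binormal correlation of 0.6 between the tests implies a correlation between the AUCs of 0.555 under the alternative and 0.570 under the null at 0.67.
- SE of the difference: 0.0435 under the null and 0.04145 under the alternative.
- Power = Φ[(0.12 − 1.96 × 0.0435)/0.04145] = Φ(0.84) = 79.9%, which reproduces the stated 80.2% closely. The sample size is not in question.

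The documents give no missed-scan or miscarriage rate, so **every rate below is an assumption**.

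**5.2 read literally.** Drop 10% or 20% of the 75 non-pregnant women at random and keep all 61 pregnant women. PPV and NPV are shown at an assumed sensitivity and specificity of 0.70, so PPV = 42.7/(42.7 + 0.3 N−) and NPV = 0.7 N−/(0.7 N− + 18.3).

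| Loss | N− | Pregnant share | Power | PPV | NPV |
|---|---|---|---|---|---|
| 0% | 75 | 44.9% | 79.9% | 65.5% | 74.2% |
| 10% | 68 | 47.3% | 78.5% | 67.7% | 72.2% |
| 20% | 60 | 50.4% | 76.5% | 70.3% | 69.7% |

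Other variance formulas and correlations, starting from 61/75 or from the full enrolment of 152 split 68/84, give a cost of 1 to 2 points at 10% and 2 to 4 points at 20%. Starting from 68/84, with Hanley-McNeil and r = 0.55, power is 86.1%, 85.0% and 83.4%.

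The AUC is the probability that a pregnant woman's marker exceeds a non-pregnant woman's. It does not depend on the ratio of the groups, so random loss does not bias it. Bias needs missed scans to be related to marker level within an outcome group. In a binormal simulation only women negative for hCG on day 11 went unscanned. With assumed correlations between day-11 hCG+β and the day-4 markers from −0.2 to 0.6, the AUC difference of 0.120 became 0.118 to 0.124 at 10% loss and 0.114 to 0.129 at 20%. With zero correlation it did not move.

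**7.3 with miscarriages coded negative.** Expected number = 61 × missed-scan rate × later-miscarriage rate. The range is 61 × 0.05 × 0.10 = 0.3 to 61 × 0.20 × 0.20 = 2.4, if neither the day-28 scan nor the Visit 6 category is used. If k such women have day-4 values like those of other pregnancies, each contributes an AUC of 0.5 for both markers, so the difference becomes 0.120 × 75/(75 + k):

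- k = 1: 0.118, power 78.4%
- k = 2: 0.117, power 76.8%

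From 84 non-pregnant women the same steps give 0.119 and 0.117.

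**The case against.** The strongest reply has three parts.

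- **5.2 may not depend on the outcome.** Its closing words, about the question of ongoing pregnancy, fit a status that may be yes or no. On that reading nobody is dropped for being non-pregnant, and the main difference from 7.3 is the day-28 route. This stands as a possible reading, so a reader should not infer that 5.2 certainly keeps only women later found pregnant. The mismatch over day 28 remains either way.
- **7.3 prescribes no miscoding.** It defines who belongs to a population, says only that the assessment can be replaced, and leaves coding to 5.1. A miscoded woman must have missed the day-21 scan and miscarried, her day-28 scan must show no sac or be ignored, and her Visit 6 category must be ignored. The two scan windows meet at day 25 (21 + 4 and 28 − 3). This also stands: the error is allowed, not ordered. No rule prevents it, however.
- **The effect is small.** At 10% loss the set loses about 8 of 84 non-pregnant women, within the planned allowance of 16 of 152. This stands for modest rates.

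A reader might also infer that the rules favour hhCG or inflate type I error. The documents do not support that. Random loss leaves the AUCs alone, marker-related loss can move the difference either way, and under equal AUCs the dilution above leaves a difference of zero.

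The ultrasound at the final visit in 2.1 may be left over from renumbering after a visit was added. It matters here only for what a day-65 assessment consists of.

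**Conclusion.** The point holds as an inconsistency in the definition of the primary analysis set and in the coding of its outcome. For a woman without a day-21 scan, 5.2 and 7.3 admit different women, and both replace a sac-based endpoint with a heart-beat state that 5.1 defines only for day 65 or later. Confidence in the mismatch is high. That 5.2 excludes non-pregnant women depends on the literal reading, and the miscoding under 7.3 is permitted rather than required.

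The size is unknown because no missed-scan rate is given, and it is probably small at modest rates. On the assumed rates the cost is a few points of power, a shift in PPV and NPV (if those secondary analyses use the same set), and about 0.001 to 0.002 of AUC difference per miscoded woman. This should be fixed because the primary set must have one definition, not because a large numerical effect has been shown.

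**What to change.** Before the hhCG results are released, put one rule into 5.1, 5.2 and 7.3. If the day-21 ultrasound is missing:

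1. The outcome is positive if a sac or heart beat is seen on the day-28 ultrasound or on any later recorded ultrasound.
2. Otherwise it is negative if the day-28 ultrasound shows no sac and the Visit 6 category is not first-trimester miscarriage.
3. A day-65 result of not ongoing does not by itself make a woman negative.
4. Otherwise the primary outcome is missing.

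In addition:

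- In 7.3, replace the reference to ongoing pregnancy on day 28 by the sac or heart-beat finding.
- State which value ectopic pregnancy takes in the binary primary outcome.
- Report how many women were classified without a day-21 scan, by outcome.
- Add a sensitivity analysis restricted to women with an observed day-21 scan.
- Reconcile 2.1 with 2.4, 5.1 and the schedule on whether an ultrasound is recorded on day 65.

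The cost is wording and slightly more analysis work. The day-28 ultrasound and the Visit 6 category are already scheduled, and a later ultrasound is used only if one is recorded. Two limits remain: a few women with neither scan stay out of the primary analysis, and an undocumented loss before day 28 would still be coded negative.
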